7.4 Criteria for withdrawal / discontinuation of participants

Participants may discontinue the trial at any time or withdraw consent. Furthermore, the treating physicians may request study discontinuation in case of significant deterioration of the condition at any time during the intervention period. All data from subjects in the intent-to-treat population, who received at least one dose of rTMS will be further used in the analyses. We will apply the last-observation-carried-forward (LOCF) method in the final analyses. In case a patient withdraws consent before the first rTMS stimulation, we will recruit an additional patient. The number of all patients recruited and randomized will be reported in the publications. All data from neuroimaging acquisition and motor behaviour will be used whenever possible, e.g. for analyses of baseline associations between brain imaging and behavior. In case of withdrawal due to adverse events or serious adverse events there will be follow-up examinations after 14 days and repeatedly until the problem is resolved, see 9.2.5.

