11. STATISTICAL METHODS

A two-tailed p-value of $< .05$ is considered to be statistically significant in all analyses. We will also report effect sizes for the comparisons of primary and clinical secondary outcome variables between groups.

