11.2 Determination of Sample Size

The main effects of the 3-week interventions on PS (SRRS scores) will be calculated in a repeated measures design including 2 measures (Baseline, week 3) and four groups (If-rTMS, iTBS, sham, waiting group-If-rTMS). Assuming a moderate effect size ($f = 0.23$) as indicated by our pilot data in a repeated measures ANOVA with moderate correlation between time points (0.5), a power of 0.95 and an $\alpha = 0.05$, we would need 88 patients (22 per group).

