11.5 Handling of missing data and drop-outs

We will apply the last-observation-carried-forward (LOCF) method in the final analyses. In case a patient withdraws consent before the first rTMS stimulation, we will recruit an additional patient. The number of all patients recruited and randomized will be reported in the publications.

Sensitivity analyses will be performed in order to establish whether premature dropout would influence the results. Therefore, the primary analyses will be repeated with all subjects who completed the interventional trial. Further tests will establish whether drop-outs differ from completers in basic clinical or demographic variables.

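### Neither the drop-out tests nor the completer re-run in section 11.5 can establish that drop-out left the SRRS result unaffected

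*Combined protocol and SAP*

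**What the plan says.** Section 11.5 of the combined protocol and SAP sets the main approach: "We will apply the last-observation-carried-forward (LOCF) method in the final analyses". It then gives a purpose, "Sensitivity analyses will be performed in order to establish whether premature dropout would influence the results", and two tools. First, "the primary analyses will be repeated with all subjects who completed the interventional trial". Second, "Further tests will establish whether drop-outs differ from completers in basic clinical or demographic variables". It names no variables, tests, split by arm, effect-size limit or confidence interval for the second tool.

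Section 11 supplies the only general criterion: "A two-tailed p-value of $< .05$ is considered to be statistically significant in all analyses". It also promises effect sizes, but for comparisons of primary and clinical secondary outcomes between groups, not for drop-outs against completers.

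Section 7.4 matters for the mechanism of drop-out: "the treating physicians may request study discontinuation in case of significant deterioration of the condition at any time during the intervention period". Section 11.4.1 only refers back to 11.5. No section plans an analysis under a different missing-data assumption.

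**The concern.** Section 11.5 asks the two checks to settle whether drop-out affected the result. A significance test can reveal a difference between drop-outs and completers. With few drop-outs it cannot show that there is none. The completer re-run replaces one assumption (the last score would have stayed the same) with another (completers represent everyone in their arm) and examines departures from neither. If drop-out is related to the course of the illness, a report could call the SRRS result unaffected on evidence that does not support it.

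**Working it through.** **The plan's own figure.** Section 11.2 reads "Assuming a moderate effect size ($f = 0.23$) as indicated by our pilot data", with correlation 0.5, power 0.95, alpha 0.05 and 88 patients (22 per group). For the group-by-time interaction with m = 2 time points, λ = f²·N·m/(1−ρ) = 0.0529 × 88 × 2 / 0.5 = 18.62, with 3 and 84 degrees of freedom. Power is 0.957, and 88 is the smallest multiple of four that reaches 0.95. The figure reproduces, so N = 88 is used below.

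**Power of the drop-out tests.** Inputs: N = 88 (11.2) and two-sided 0.05 (11). Two inputs are assumptions because the documents do not give them: k drop-outs (9, 13 or 18, about 10%, 15% and 20%) and the difference d (0.5 or 0.8 SD). For a two-sample t-test, λ = d²·k(88−k)/88 with 1 and 86 degrees of freedom. For k = 9 and d = 0.5, λ = 0.25 × 9 × 79 / 88 = 2.02, which gives power 0.29. The 95% CI half-width in SD units is t(0.975; 86)·√(1/k + 1/(88−k)). For k = 9 this is 1.99 × √(1/9 + 1/79) = 0.70.

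| Drop-outs / completers | Power, 0.5 SD | Power, 0.8 SD | 95% CI half-width | Difference detectable with 80% power |
|---|---|---|---|---|
| 9 / 79 | 0.29 | 0.61 | ±0.70 SD | 1.00 SD |
| 13 / 75 | 0.38 | 0.75 | ±0.60 SD | 0.85 SD |
| 18 / 70 | 0.46 | 0.85 | ±0.53 SD | 0.75 SD |

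Over a wider range, power for 0.5 SD is 16% with 4 drop-outs, 52% with 22 and 62% with 35. Even an observed difference of zero would leave 0.5 SD inside the interval at up to 20% drop-out.

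**The completer re-run.** Low power is not its problem. By the formula above, power for f = 0.23 is 0.93, 0.90 and 0.85 with 79, 70 and 62 completers. Its weakness is the assumption it makes, shown by an illustrative simulation. All inputs except the 22 per arm and the correlation of 0.5 are assumed: lf-rTMS against placebo, no true effect, and the 4 worst-worsening lf-rTMS patients and 1 such placebo patient leaving after the week-1 rating (4/22 = 18%; 1/22 = 5%). Higher SRRS is worse, so a negative bias favours lf-rTMS.

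| Who stops, and what is carried forward | Completer bias | LOCF bias | Both falsely significant |
|---|---|---|---|
| Worst change by week 3, not yet seen; week-1 score | −0.22 SD | −0.08 SD | about 7% |
| Worst change already seen at week 1; week-1 score | −0.11 SD | +0.08 SD | about 2% |
| Worst change by week 3; exit before any post-baseline rating, baseline score | about −0.22 SD | −0.16 SD | about 13% |

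Rejection rates, against a nominal 5%, are about 14% (completers) and 8% (LOCF) in the first row, and about 7% and 4% in the second. The sign of the LOCF bias turns on whether the carried score already contains the worsening. Reversing the 4-to-1 split reverses all the signs.

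**The case against.** Much can be said for the plan. The documents give neither a drop-out rate nor a relevant difference, and for 0.8 SD the tests do reasonably well from 9 drop-outs upward. SRRS is rated weekly in groups 1–3, so LOCF may carry a score that already shows the deterioration. Section 3.7 reports no case of deterioration in the prior trial with the same stimulation. Reasons for discontinuation go into the CRF (12.1.1), and numbers recruited and randomised will be published. The completer re-run can be compared with the LOCF result by effect size, not only by p-value. A tipping-point analysis is one acceptable sensitivity analysis among several.

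These points limit the concern, and they rule out some stronger readings that a reader might infer:

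- *Completer and LOCF analyses are always biased in the same direction.* They are not: the second row of the simulation gives opposite signs.
- *A false lf-rTMS benefit would pass both checks.* This is not shown. Both are falsely significant in about 2% to 13% of runs, depending on the mechanism, and the direction depends on an assumed imbalance that has no source in the documents.
- *The tests use only baseline data pooled over arms.* Section 11.5 says neither.
- *The sponsor will read non-significance as robustness.* No such rule is written. It is a natural inference from the verb used and the lack of another criterion, but still an inference.

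What remains is that neither check examines a departure from its own missing-data assumption, and nothing else in the documents does.

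**Conclusion.** The concern holds in a limited form: the two checks cannot deliver the conclusion that section 11.5 assigns to them. For the tests, this rests on assumed drop-out of 10% to 20% and a moderate difference of 0.5 SD, where a test misses 54% to 71% of the time. For large differences the tests usually succeed. For the completer re-run, it rests on drop-out being related to deterioration, which section 7.4 makes possible but the documents do not quantify. The simulated biases, up to about 0.2 SD, illustrate assumed mechanisms and do not predict this trial. The sample size and the primary model are unaffected; only the robustness statement is.

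**What to change.** Amend section 11.5 as follows:

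1. Remove the claim that tests settle whether drop-outs and completers are alike. Name the variables. Report drop-out numbers and reasons by arm, and standardised differences with 95% CIs in place of p-values.
2. Keep the completer re-run as a supplement.
3. Add a pre-specified delta-adjusted analysis of the week-3 SRRS comparison, at least for lf-rTMS against placebo (Hypothesis 1a). Impute missing week-3 scores from the baseline, week-1 and week-2 SRRS, shift the imputed values by a stated series of deltas that may differ by arm, and report the delta at which the conclusion changes. Call the result robust only if that delta is implausible. The waiting group has no week-1 or week-2 rating (9.1.2), so only baseline is available for it.

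Fix the deltas before the first interim analysis in section 11.4.4, because deltas chosen after seeing results carry less weight. The cost is some wording and one analysis on data already being collected. The robustness statement may become less favourable.

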12. QUALITY ASSURANCE AND CONTROL

All study personnel will be trained by the PI to achieve consistent adherence to procedures and interrater reliability. Standard operating procedures will be written for the intervention and standardized TMS measurements. For all clinical rating scales, instructions and manuals are provided for the study personnel. All study personnel will have to read the manuals.

12.1 Data handling and record keeping / archiving

12.1.1 Case Report Forms

All relevant data is documented in paper CRFs. This data includes inclusion/exclusion criteria, demographic data, medical history, scores of clinical and motor rating scales. Furthermore, side effects, concomitant treatment, reasons for discontinuation will be recorded in the CRF. Timing and conductance of experimental measures, such as posturography, cerebral MRI, cortical excitability, and actigraphy will be recorded in the CRF. However, the real data of these measures is stored electronically outside the CRF.

For each enrolled study participant a CRF is maintained. CRFs will be kept current to reflect subject status at each phase during the course of study. Participants will be coded by use of a participant number in combination with the year of birth.

The paper forms of rating scales (e.g. PANSS) and the electronic data (e.g. MRI, posturography, ect.) are considered source documents. Furthermore, in patients the medical record of our hospital is a source document for the past psychiatric history and current concomitant treatment. All other data (participant history, side effects, ect.) are directly entered into the CRF without further source.

The study personnel is authorized to enter data into the CRFs, the name of the entering person will be documented. CRF data will be recorded in an electronic database, i.e. RedCap-Database. The procedure will include data cross-check between electronic and paper CRF. Any deviation will be corrected by consensus and consulting the CRF forms. RedCap-Database has individualized logins for each member of the study team and provides logs for data entry.

The electronic database for the non-CRF data will be logged via a secure Dropbox folder, thus the person entering the data or changing data can be identified by individualized logins. The log also identifies the document changes and the time of the change. Dropbox allows for restoring each version of the documents within the study folder. A copy of the electronic neuroimaging data will be shared with Collaborator [name], College Station, TX, USA. At her laboratory, specific neuroimaging analyses will be performed with a subset of the electronic data. The original electronic files will be stored in Bern (see 12.1.3), while the specific neuroimaging analyses data of [name] will be stored encrypted at her university for 10 years.

12.1.2 Specification of source documents

As described in 12.1.1. most data in the CRFs is source data. Furthermore, Informed consent form, specific rating scales and electronic data (such as MRI, actigraphy or posturography) are source data. In patients, the medical record of the hospital may contain source data on the psychiatric history. All CRFs and paper source data will be kept in folders. Any extra examination in case of additional safety assessments will be documented on paper and kept as source data in the same folders as CRF and other source data.

12.1.3 Record keeping / archiving

All study data will be archived for 10 years after study termination or premature termination of the trial at the translational research center of the University Hospital of Psychiatry, Bern. In addition, the data of specific neuroimaging analyses performed at [name] laboratory, will be stored encrypted for 10 years at Texas A & M University, College Station, TX, USA. Thus, source data are kept in Bern, and all further handled data will be stored under identical conditions in Bern or Texas Station.

12.2 Data management

Data of all participants will be encrypted and analysis will be performed using encrypted data only. Unblinding of participant-specific data is only possible after consent has been given by the participants and the sponsor. Data of all participants will receive a numerical identification. The key to this encryption code will be stored in a single file at the address below, and it will be accessible only by the sponsor and the principal investigator.

12.2.1 Data Management System

Describe what system (also software) is being used and who is responsible and how it is tested before the trial (may include a description of where the system is hosted).

12.2.1.1 Neuroimaging data

MRI data are anonymized digital data of appr. 1 GB per subject and scan, we will aim for 278 scans, i.e. total of 300 GB. MRI data sets include the dicom files of the planned sequences fMRI task, fMRI rest, ASL rest, DTI and T1 anatomy. MRI data sets will be safely stored in encrypted formats at the server of the translational research center, university hospital in Bern. Data will be logged with personal logins, such that any change to the files is reproducible. Data analysis will be performed locally in computers of the institute's network. Some analyses are planned to be performed on encrypted data at computers of the study collaborator [name]. All files generated during data processing and analysis will be stored. Total data volume is approximately 2 TB. Neuroimaging data will be stored at a dropbox-folder, which is encrypted by Boxcryptor Software and owned by the Translational Research Center, University Hospital of Psychiatry, Bern. The system has been effectively used in several studies. Access to the folder and files is secured by personal login and password. The log of the Dropbox folder enables the identification of data entry/data change according to the logins used. The log will inform on which data has been changed when by whom. Dropbox allows for restoration of each file version, thus each change can be tracked.

12.2.1.2 motor behavioral/instrumental data

Data from actigraphy, posturography, TMS-MEP experiments as well as video recordings of coin rotation will be stored encrypted in digital format. As neuroimaging data, storage will comply with the federal human research act and will be conducted at standard facilities of the translational research center with encrypted and logged server storage. Data access is granted upon personal logins, such that any change to the files is reproducible. Each dataset includes several measures across 4-5 time points for one study participant. We expect appr. 1 GB per subject, total of 130 GB.

12.2.1.3 clinical and demographic data

Clinical data including outcome measures with observer based rating scales or patients' history will be collected. This data is transferred to paper case report forms and will later be anonymously transferred to a red cap data base, hosted by the CTU Bern. Data access is only available to study staff with personalized logins. During the longitudinal assessments approximately 300 variables will be assessed for each participant.

12.2.2 Data security, access and back-up

Only the PI and authorized personnel with own logins and passwords will have access to the electronic data. The translational research center Bern runs a daily backup of the dropbox folders. The RedCap Database also has regular backups.

12.2.3 Analysis and archiving

All analyses will be performed with a final copy of the SPSS file including all clinical data. All other analyses (neuroimaging, posturography, actigraphy) will be conducted with the appropriate standard software. Only the PI and authorized personnel will have access to the data to perform the analyses.

12.2.4 Electronic and central data validation

Data will be checked for consistency, e.g. range checks for questionnaire scores or test scores, checks for date entries temporal consistency.

12.3 Monitoring

The principal investigator will check the CRFs for completeness and internal consistency (plausibility of information) and external consistency (with source data) after each participant completed the study. In addition an external monitoring will be performed by [name].

Four monitoring dates are planned. The first before the study recruitment starts, the second after the first three participants have been included, the third after 50% of enrolment was achieved and the final monitoring is planned after the last data had been collected.

Before first recruitment: Check whether all study assessments and instruments are ready and complete.

After the first three participants: Check CRF entries and compliance with source data where possible. Clarify queries of data entry or study procedures.

After the 50% enrolment: Check whether CRFs of the all collected cases are completed and data is consistent.

After the final data collection: Check whether CRFs of the all cases collected after the last monitoring are completed and data is consistent.

12.4 Audits and Inspections

Not intended for this single center trial.

12.5 Confidentiality, Data Protection

All data will be handled strictly confidential. Direct access to the source documents will be permitted only for purposes of inspections (ICHE6, 6.10) by authorities such as the CEC or monitoring by the PI. Only the PI and his team will have access to the protocol, dataset and other study related information during and after the study.

12.6 Storage of biological material and related health data

No storage of biological material is planned.

All electronic data will be archived for 10 years (see 12.1).

13. PUBLICATION AND DISSEMINATION POLICY

Publication of results is the responsibility of the sponsor/investigator. The results of the study will be prepared for publication in peer-reviewed scientific journals, preferably as open-access articles. Authorship will follow the national guidelines. Furthermore, results will be reported at scientific conferences as posters or oral communications. The use of professional writers is not intended. After scientific publication, the results will be prepared for communication in lay man's terms in the media.

Data sharing outside of the project is currently not planned. However, electronic data, particularly neuroimaging electronic data, may be later shared with national or international collaborators to address research questions that are currently unknown. The data storage must comply with the same regulations as the data storage of this study.

14. FUNDING AND SUPPORT

14.1 Funding

This study receives project funding by the Swiss National Science Foundation (grant #182469 to [name]). Additional minor costs will be covered by the University Hospital of Psychiatry in Bern.

14.2 Other Support

Consumables and further material support is provided by the host institution, the Translational Research Center of the University Hospital of Psychiatry, University of Bern, Switzerland.

15. INSURANCE

No special insurance due to category A.

17. APPENDICES

1. IB (according to ISO 14155) – “Produktinformation”
2. TMS device manual
3. Case Report Forms, v2 of December 13th 2018, patient version and control version
4. Study Information for patients, v2 of December 13th 2018
5. Study Information for healthy controls, v2 of December 13th 2018
